## 6.2. Statistical analysis

All analyses will follow intention to treat such that patients will be analyzed based on the allocated intervention on the day of their ED visit (BH-VPN or treatment as usual). We will compare the two groups on age, sex, suicide ideation, and neurocognitive disorders to assess for balance, which is inferred with randomization.

The primary outcome, inpatient admission  $\leq 5$  days, will be compared between the two groups of patients using a chi-square test. We will explore differences by site by conducting stratified analysis by hospital. We will attempt to adjust for the correlation among patients seen on the same day using a generalized linear mixed model with a log link and random effect for day, nested within hospital. If convergence problems arise due to small sample sizes, we will collapse by week rather than day. We will also control for hospital as a fixed effect in the model. Results for group comparisons will be presented with odds ratios and 95% confidence intervals.

Secondary outcomes are 45-day post discharge utilization (yes/no), 90-day post discharge utilization (yes/no), QCC defined 30-day readmission (yes/no), and patient centric 30-day readmission (yes/no). Each of the secondary outcomes are dichotomous and will be compared using the same approach as the primary outcome. All tests will be two sided and the data will be analyzed using SAS Enterprise Guide version 6.1. For all outcomes, we assume if there are no visits in the CHS electronic medical record that the value for having a visit is null; therefore, there will be no missing data for the primary or secondary outcome measures.

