Study Procedures	Patients who present to the ED at one of the two participating CHS EDs with a telepsychiatric consult performed will be treated and followed per the proposed CHS behavioral health patient navigation pathway (BH-VPN) or usual care. As part of the current care process, Patients are identified by the ED physician in the ED as needing psychiatric evaluation and a referral is made to the telepsychiatric consult, the care of these patients will follow the allocated BH-VPN pathway or

	
usual care. Regardless of participation in the BH-VPN pathway or usual care, the ED providers decide based on available information the ultimate disposition for patients --discharge from the ED or admit to the hospital.
 
Patients who complete a telepsychiatric consult in the ED Monday through Friday during the hours of operation can be enrolled to either the control or intervention arm based on a randomization scheme that randomly allocates days that navigators are available. On days where the navigator is available, all patients who meet eligibility criteria will be considered exposed to the interventions; whereas, on days the navigator is not available all patients will be considered exposed to Usual care. Patients who are in the intervention arm will be offered navigation services for 45 days following ED discharge.
 
The BH-VPN pathway is defined by several key components:
 
 
• Introduction of the navigation process to the patient, while in the ED
 
• Evaluation of the patient and their needs.
 
• Follow-up evaluation within 72 hours by phone, and weekly contact with the BH-VPN until 45 days post ED discharge
 
• Confirm that a follow-up visit is scheduled and if the patient made it to the appointment.
 
• Placement into an appropriate case management program, if needed
 

Statistical Analysis
	
Analyses will include all patients identified as having completed telepsychiatric consult and meeting the additional inclusion and exclusion criteria. Comparisons of the intervention and usual care groups will be made using univariate analyses such as the t-test and chi-square test. The primary outcome, ED to inpatient conversion, will be compared between the two groups of patients using logistic regression. Results will be presented with odds ratios and 95% confidence intervals.

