#### **5.1.4. Adverse Events**

Safety/Serious Adverse Events that will be specifically monitored/evaluated include suicide ideation and death. Suicide ideation is tracked among the intervention population at each touch

point. Death rates can be compared between the usual care and intervention populations once a month using data in the Enterprise Data Warehouse. Death is noted based on notification to CHS by a friend or family member or from identification of death from the social security death index which occurs through monthly updates.

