### **6. DATA COLLECTION AND REPORTING**

Patient demographics, comorbid conditions, and utilization will be obtained from the electronic medical record and billing systems. Data from the initial assessment and follow-up contacts will be stored in HealtheCare, a care management platform in Cerner. Data will be retrieved by an application specialist on the research team. Data may be retrieved retrospective to a patient's completion of the intervention or usual care arm of the study. A monthly executive summary will be produced, showing patient volume, percent patients with suicidal ideation, and utilization.

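### Section 6.2 uses age, sex, suicide ideation and neurocognitive disorder only for a balance check; pre-specified adjustment for baseline values recorded alike in both arms could add modest power

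*Combined protocol and SAP*

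**What the plan says.** Section 6.2 gives the four variables one use: "We will compare the two groups on age, sex, suicide ideation, and neurocognitive disorders to assess for balance". It adds that balance is to be expected from the randomisation, and gives no rule for what follows if the arms differ.

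The primary outcome "will be compared between the two groups of patients using a chi-square test". Same-day correlation is then to be handled with a "generalized linear mixed model with a log link and random effect for day, nested within hospital", and the only covariate named for that model is the site: "We will also control for hospital as a fixed effect in the model". On reporting: "Results for group comparisons will be presented with odds ratios and 95% confidence intervals". The secondary outcomes follow the same approach. The Statistical Analysis entry of the protocol summary says instead that the primary outcome "will be compared between the two groups of patients using logistic regression", again without naming covariates.

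On data sources, section 6 says: "Patient demographics, comorbid conditions, and utilization will be obtained from the electronic medical record and billing systems". That sentence is not tied to one arm, but it does not mention suicide ideation. Section 5.1.4 says: "Suicide ideation is tracked among the intervention population at each touch" point. Sections 5.3, 8.1 and 8.2 place the C-SSRS within the navigator's assessments and calls.

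**The concern.** Once days have been randomised, a between-arm comparison of baseline variables does nothing for the treatment estimate. If the variables predict admission, putting them in the outcome model raises power and corrects the estimate for whatever chance imbalance occurred. The plan already intends to assemble these variables in order to compare them.

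Two things are at stake. One is some power for the primary comparison. The other is pre-specification: if the balance check shows a difference, the plan does not say whether an adjusted analysis follows, so that choice would be made after the data are seen.

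**Working it through.** **1. Reproduce the plan's sample size.** Inputs from section 6.1: 50% against 35%, α = 0.05, 85% power, equal allocation, chi-square test. Two-sided testing is from section 6.2.

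- Uncorrected, per arm: n = [1.960·√(2·0.425·0.575) + 1.036·√(0.25 + 0.2275)]² / 0.15² = 193.5, so 194 per arm and 388 in total.
- With continuity correction: n/4 · [1 + √(1 + 4/(n·0.15))]² = 206.6, so 207 per arm and 414 in total. This matches the plan exactly.
- Clustering: 414 × 1.1 = 455.4, so 456. This also matches.

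**2. Power with adjustment.** Effective N = 456 / 1.1 / (1 − R²), entered into the same continuity-corrected formula. R² is an assumption; the documents report no association between any of the four variables and 5-day admission. The N for the plan's power is 414 × (1 − R²) × 1.1, and the risk-difference interval scales by √(1 − R²).

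| R² (assumed) | Effective N | Power | N for the plan's power | Risk-difference CI width |
|---|---|---|---|---|
| 0 | 414.5 | 85.1% | 456 | × 1.000 |
| 0.02 | 423.0 | 85.9% | 447 | × 0.990 |
| 0.05 | 436.4 | 87.0% | 433 | × 0.975 |
| 0.10 | 460.6 | 88.8% | 410 | × 0.949 |
| 0.20 | 518.2 | 92.2% | 365 | × 0.894 |

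To give R² a scale: near a 50% admission rate, one binary covariate with 50% prevalence that shifts admission by δ has R² ≈ δ². Shifts of 20 and 30 points therefore give about 0.04 and 0.09. These shifts are illustrations, not figures from the documents.

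**3. What happens to the odds ratio.** Simulation of 4,000 trials per scenario, each with 414 independent patients, comparing the unadjusted (uncorrected) test with adjusted logistic regression:

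| R² | log OR, unadjusted → adjusted | SE of log OR | Power | Variance ratio, standardised / unadjusted risk difference |
|---|---|---|---|---|
| 0.02 | −0.626 → −0.641 | 0.202 → 0.205 | 88.4% → 88.6% | 0.986 |
| 0.06 | −0.627 → −0.664 | 0.202 → 0.209 | 87.6% → 89.5% | 0.948 |
| 0.11 | −0.619 → −0.698 | 0.202 → 0.216 | 87.1% → 90.8% | 0.887 |

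The standard error of the log odds ratio rises slightly. Power increases because the conditional odds ratio lies further from 1. Only the standardised risk difference becomes more precise. Power levels here exceed those in step 2 because this test has no continuity correction.

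**4. Chance imbalance.** Assume a covariate with 50% prevalence, and apply the plan's design effect of 1.1 to it. The SD of the between-arm difference in prevalence is √(4 × 0.25 × 1.1 / 456) = 0.049. A 2-SD imbalance is 9.8 points. If the covariate shifts admission by 20 or 30 points (assumed), the unadjusted risk difference moves by 0.098 × 0.20 = 2.0 or 0.098 × 0.30 = 2.9 points, that is 13% or 20% of the 15-point target.

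**5. Which variables can be used.** Age, sex and, as a comorbidity, neurocognitive disorder fall under the record sources named in section 6. Neurocognitive status also decides whom the navigator approaches in the intervention arm (sections 4.4 and 5.3), so it could be noted more thoroughly there unless both arms are read from the same record fields. For suicide ideation, the planned comparison implies a two-arm source, but the only measurement described is in the intervention arm.

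**The case against.** The strongest reply is that this is an efficiency preference. The sample size was calculated for an unadjusted chi-square, section 6.2 names that test, and under day-level randomisation it is not biased by leaving covariates out. The plan also never says the balance check will drive a decision. All of this stands. Chance imbalance is already part of the unadjusted standard error; adjustment improves the estimate in hand but does not repair a flaw.

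The second reply is that the gain rests on an R² that nobody has estimated. That stands too, which is why a range including zero is shown.

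Several stronger readings are tempting, and the documents do not support them:

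- *All four variables are available in both arms.* This is not shown for suicide ideation. Adjusting for a value measured by the navigator, after allocation and in one arm only, could introduce a bias that the present plan does not have.
- *Power is really below 80%, so adjustment is needed.* That needs a design effect of 1 + (3.7 − 1) × 0.1 = 1.27, taking the 3.7 patients per day for both hospitals in section 5.2 as the cluster size. Section 6.1 uses 1.1. Which is right is a separate clustering question, and this point does not depend on it: at 456 patients and 1.27 the gain at R² = 0.05 is of similar size (79.3% to 81.5%).
- *The reported confidence interval would be narrower.* Not for the odds ratio (working, step 3).
- *The change is free.* A chi-square cannot take covariates, so the primary comparison moves to a model, and section 6.2 already foresees convergence problems.

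**Conclusion.** The point holds as a modest, worthwhile improvement. No outcome model uses the four variables. Their omission causes no bias, but it gives up some power and leaves chance imbalance uncorrected.

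On the plan's own inputs the gain is about 1 point of power at R² = 0.02, 2 at 0.05, 4 at 0.10, and none if the covariates do not predict admission. This rests on the assumed R², on the plan's design effect of 1.1, and on covariates that are true baseline values ascertained alike in both arms. The case for pre-specifying the choice does not depend on R².

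A reader might infer that the planned analysis is invalid or that the trial is underpowered for this reason. Neither follows.

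**What to change.** In section 6.2:

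- Pre-specify age, sex and neurocognitive disorder as fixed covariates beside hospital in the day-clustered model, for the primary and secondary outcomes. Take them from the EMR or billing record, with the same fields and look-back in both arms.
- Add suicide ideation only if the index ED record holds a measure taken before navigator contact and recorded identically in both arms. Otherwise leave it out of the model; a balance comparison on it would then be hard to interpret as well.
- State that this adjusted model, not the plain chi-square, carries the primary comparison, and bring the protocol summary into line.
- Report a standardised risk difference beside the odds ratio, and name the method for its variance allowing for day clustering. State the link function at the same time, since a log link does not yield the odds ratios that the section promises.
- Name the fallback if the adjusted model does not converge. Keep the baseline table as description.

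Cost: a few sentences, no extra patients, and little extra data work where the variables are already to be extracted for the balance comparison. The downsides are small. The adjusted odds ratio is conditional, which the standardised risk difference offsets, and a few more fixed effects add slightly to the convergence risk that the plan already anticipates.

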## **5.2. Randomization and Allocation**

Randomization for the purposes of this project, will be based on days the Navigators are available to treat patients who've completed their telepsychiatric consult per the BH-VPN or usual care. Patients may be in the ED for multiple days. Their enrollment status depends on the day and time of their initial telepsychiatric consultation. Navigation will only be available for those patients whose consult occurs during intervention day/times. As part of the research design and rollout of this project, randomization will occur at the day level with the days being identified as intervention or usual care days for the duration of the study. We expect an average of 3.7 patients seen daily for both hospitals combined. Patients will accrue in both arms of the study Monday through Friday during the hours of operation. Patients will not be accrued on days where the navigators are not available such as weekends, nights, and holidays.

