## 6.1. Sample size analysis and statistical analysis

We are conducting the study for about 6 months leading to approximately 6 months\*4 weeks\*5 days=120 days with 60 days allocated to intervention and 60 allocated to treatment as usual. This study is designed to detect a 15% absolute reduction in the inpatient admission within 5 days of index ED presentation with the usual care group assumed to have a 50% inpatient admission rate (internal report). We will have 85% power to detect this reduction with a total sample size of 414 ( $\alpha=0.05$ ) using a Chi-square test for independence. We will not need to adjust for attrition as the primary outcome of inpatient admission <5 days is obtainable from electronic health records for all individuals. To account for the possible correlation among patients seen in the ED on the same day, we have inflated the sample size by 10% assuming the average number of patients per ED per day is 2 and the intra-class correlation coefficient=0.1 (Design effect=1+(2-1)ICC). Therefore, our target sample size is N=456.

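### The primary outcome is tied to a chi-square test that ignores the randomised day, the day-level model is only attempted, and nothing says which analysis decides the trial

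*Combined protocol and SAP*

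**What the plan says.** **Unit of randomisation.** Section 5.2 states that "randomization will occur at the day level with the days being identified as intervention or usual care days for the duration of the study". It also gives a combined volume: "We expect an average of 3.7 patients seen daily for both hospitals combined". Section 6.1 counts about 120 days, 60 per arm.

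**Sample size.** Section 6.1 states "We will have 85% power to detect this reduction with a total sample size of 414", at alpha 0.05 with a chi-square test, for 50% versus 35%. The total is then raised by a tenth to allow for same-day correlation, and the inputs for that step are stated: "assuming the average number of patients per ED per day is 2 and the intra-class correlation coefficient=0.1". The target is 456.

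**Analysis.** Section 6.2 says the primary outcome "will be compared between the two groups of patients using a chi-square test". Later in the same paragraph it says "We will attempt to adjust for the correlation among patients seen on the same day". The tool is a mixed model on the log scale in which day, within each hospital, is the random term. Hospital is also a fixed effect. If the model does not converge, week replaces day. Results are to be given as odds ratios with 95% confidence intervals. The four secondary outcomes follow the same approach.

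**Summary.** The Statistical Analysis entry of the Protocol Summary lists the chi-square among univariate comparisons and assigns the primary outcome to logistic regression, with no term for day.

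**The concern.** The chi-square test takes each patient as an independent observation, although allocation is by day and the plan itself expects outcomes on the same day in the same ED to be correlated. Under that correlation the difference between arms varies more than the test assumes, so a nominal 5% test can reject too often. The 10% inflation adds patients. It does not change the test's standard error formula.

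Three analyses are therefore candidates for the primary result: the chi-square, the mixed model, and the logistic regression of the Summary. If they disagree, the documents do not say which one counts, and the choice could follow the data. The secondary outcomes inherit the same open choice. No error size can be given for them, because the documents state no ICC for those outcomes.

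Two details of the model add to this. The week fallback may drop the randomised unit, and a log link yields risk ratios where odds ratios are promised.

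**Working it through.** **1. Reproduce the plan's figures.** Inputs from Section 6.1: 50% versus 35%, 85% power, alpha 0.05. Section 6.2 makes all tests two-sided.

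- Without continuity correction: n per arm = [1.96·√(2·0.425·0.575) + 1.036·√(0.25 + 0.2275)]² / 0.15² = 193.5, so 194 per arm and 388 in total.
- With continuity correction: n′ = (193.5/4)·[1 + √(1 + 4/(193.5·0.15))]² = 206.6, so 207 per arm and 414 in total. This matches the plan, so the stated size corresponds to the corrected test.
- Design effect (DE) = 1 + (2 − 1)·0.1 = 1.10, and 414 × 1.10 = 455.4, given as 456.

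**2. True error of the unadjusted test.**

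- Uncorrected: 2·[1 − Φ(1.96/√DE)].
- Continuity-corrected, with 228 per arm and a rate of 50%: SE = √(0.25·2/228) = 0.0468 and the correction is 1/228 = 0.0044. The threshold rises to 1.96 + 0.0044/0.0468 = 2.054, and the error is 2·[1 − Φ(2.054/√DE)].

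| Setting, ICC 0.1 | DE | Uncorrected | Corrected |
|---|---|---|---|
| Plan's inputs: 2 per ED-day | 1.10 | 6.2% | 5.0% |
| Sensitivity: Poisson counts, mean 1.9 per ED-day | 1 + 1.9·0.1 = 1.19 | 7.2% | 6.0% |
| Sensitivity: ICC fully shared across EDs, 3.7 per day | 1 + 2.7·0.1 = 1.27 | 8.2% | 6.8% |
| Sensitivity: fully shared, Poisson, mean 3.8 per day | 1 + 3.8·0.1 = 1.38 | 9.5% | 8.0% |

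The mean of 1.9 is 456/240 ED-days. Only the first row uses the plan's inputs alone. Poisson counts and sharing across EDs are assumptions of this check.

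**3. Simulation check.** Null simulation with 120 days (60/60), two EDs, a rate of 50%, a beta-binomial day effect and ICC 0.1 gives, uncorrected and corrected:

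- within ED-day: 6.2% and 5.1% with fixed counts, 7.2% and 6.0% with Poisson counts;
- fully shared: 8.6% and 7.2% with fixed counts, 9.6% and 8.1% with Poisson counts.

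At ICC 0.01 within ED-day the figures are 5.0% to 5.2% and 4.1%, so there is no material excess. Standard errors clustered by calendar day hold 5.1% (ED-day) and 5.2% (shared) with Poisson counts.

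**4. The planned model and its fallback.** Likelihood-ratio tests with Poisson counts, ICC 0.1 within ED-day and a simulation error of about 0.3 points:

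- Day within hospital: 5.3% with the log link, 5.2% with a logit link.
- Week within hospital as the only random effect (logit): 6.9%, close to the uncorrected chi-square. A week can contain days from both arms, so a week effect does not represent correlation within a day.
- Week-by-arm clusters within hospital (logit), the other possible reading: 5.3%.

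**5. Link and effect measure.** At the planning rates, RR = 0.35/0.50 = 0.70 and OR = (0.35/0.65)/(0.50/0.50) = 0.54. A log-link model estimates the first; Section 6.2 promises the second.

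**The case against.** The plan does not overlook clustering. It inflates the sample size for it and describes a model whose day-within-hospital effect matches the ED-day correlation of Section 6.1. That model holds close to 5% under that structure. The cautious verb may be no more than a convergence caveat. The Summary, which puts the chi-square among univariate comparisons and the primary outcome under regression, supports reading the chi-square as a first look and the model as the source of the reported estimate. With the continuity-corrected test and the plan's own inputs, the error is 5.0% in any case.

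Most of this stands, and it limits the size of the point. It does not supply the missing designation: Section 6.2 ties the primary outcome directly to the chi-square, Section 6.1 bases power on it, and the regression in the Summary has no day term.

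A reader might infer three stronger things that the documents do not support.

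- **An error near 10%.** This needs one allocation covering both EDs and the full ICC shared between them. The 120 days split 60/60 suggest a common allocation, but no section states it, and Section 6.1 defines the correlation per ED. With a between-ED correlation of only 0.02 and Poisson counts, DE = 1 + 1.9·0.1 + 1.9·0.02 = 1.228, giving 7.7% uncorrected and 6.4% corrected.
- **An inadequate day-within-hospital model.** It is adequate under the plan's own assumption. Clustering on calendar day is a safeguard in case correlation crosses the EDs.
- **A log link that distorts the error rate.** It is a reporting mismatch, and possibly a slip for logit.

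**Conclusion.** The point holds as a gap in the specification of the primary analysis, and it should be fixed. The named test ignores the randomised unit, the analysis that respects it is not made binding, and the documents do not rank the candidates.

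If the chi-square decided the trial, its two-sided error would be about 6.2% uncorrected or about 5.0% continuity-corrected. This rests on the plan's ICC of 0.1 and two patients per ED-day; Section 6.2 does not say which version would be used. The higher figures are sensitivity results only: 7.2% and 6.0% with Poisson counts, and about 8% to 10% uncorrected or 7% to 8% corrected with full sharing across EDs.

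The missing designation matters at any ICC. The week fallback is a lesser matter, since it applies only if the day model fails and has one reading that keeps the error near 5% within ED-day.

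**What to change.** - In Section 6.2, name the day-adjusted mixed model, with hospital as a fixed effect, as the single primary analysis of the primary outcome. Make the chi-square descriptive and state whether it is continuity-corrected.
- State whether one day allocation covers both EDs, and cluster on the unit actually randomised: calendar day if it does.
- Replace the week fallback with one that keeps the day, such as cluster-robust errors by day or a permutation test that re-allocates days.
- Match link and effect measure: logit with odds ratios, or log with risk ratios.
- Align the Protocol Summary and the secondary outcomes with this choice.

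**Cost.** Wording and a few lines of code, with no new data. Intervals become slightly wider. In simulation at about N=456 (50% versus 35%, ICC 0.1, Poisson counts), power with calendar-day robust errors is about 84% if correlation stays within ED-day, against the planned 85%, and about 78% to 79% if it is fully shared across EDs. The chi-square shows 88% and 86% uncorrected, or 86% and 84% corrected, but with these variable counts its error exceeds 5% in both structures.

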## **4.2. Participating Sites**

Patients will be exposed to the intervention or usual care at two participating ED's in Carolinas HealthCare System. The following Carolinas Healthcare System ED sites will be participating in this project.

- Carolinas HealthCare System Pineville
- Carolinas HealthCare System Union

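### Site differences are to be explored only through separate hospital analyses; no planned analysis directly estimates or tests whether the navigation effect differs between the two hospitals

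*Combined protocol and SAP*

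**What the plan says.** Section 4.2 names two hospitals: "Patients will be exposed to the intervention or usual care at two participating ED's in Carolinas HealthCare System". On comparing them, section 6.2 has one sentence, "We will explore differences by site by conducting stratified analysis by hospital", and then, for the mixed model, "We will also control for hospital as a fixed effect in the model". That model also has a random effect for day nested within hospital. Group comparisons are to be reported as odds ratios with 95% confidence intervals.

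The documents name no arm-by-hospital interaction or other heterogeneity test, and give no rule for reading the two hospital results together. The objectives and hypothesis in section 1 contain no site-specific question. Section 6.1 sets the sample size for the pooled comparison and gives neither power per hospital nor the expected split of patients between hospitals.

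**The concern.** The stated aim is to learn about differences by site. Two separate comparisons give two effect estimates, not an estimate of the gap between them or its uncertainty. A main effect for hospital allows the baseline admission rates to differ but holds the navigation effect common to both sites. The aim therefore has no analysis that answers it directly.

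With two sites, each holding about half the patients, it is easy to summarise the result as the programme working at one and not at the other. That pattern is common by chance even when the true effects are equal. Section 6.2 also says the secondary outcomes will be compared in the same way as the primary. Read literally, this extends the hospital-by-hospital comparisons to four more outcomes. Two of these, the readmission measures, apply only to patients who were admitted (section 5.1.2), so the numbers per site are smaller still.

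**Working it through.** **Inputs from section 6.1.** Usual-care rate: "with the usual care group assumed to have a 50% inpatient admission rate (internal report"). Effect: "This study is designed to detect a 15% absolute reduction in the inpatient admission within 5 days of index ED presentation", so 50% v 35%. Days are allocated 60:60, the ICC is 0.1 with 2 patients per ED per day, giving a design effect of 1.1, and the target is N = 456. **From section 6.2:** "All tests will be two sided", and the primary outcome "will be compared between the two groups of patients using a chi-square test". **Assumed, not in the documents:** an equal split between hospitals. It is compatible with the single figure of 2 patients per ED per day in section 6.1 and the 3.7 per day for both hospitals in section 5.2.

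**Reproducing the plan's figure.** The plan states "We will have 85% power to detect this reduction with a total sample size of 414". The two-proportion formula at two-sided 0.05 and 85% power, with continuity correction, gives 207 per arm, or 414. Without the correction it gives 388. Then 414 × 1.1 = 455.4, rounded up to 456. Both figures reproduce.

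**Power in one hospital.**
- Effective patients per arm per hospital: 456 / 1.1 / 4 = 103.6.
- SE under the null: sqrt(2 × 0.425 × 0.575 / 103.6) = 0.0687.
- SE under the alternative: sqrt((0.25 + 0.2275) / 103.6) = 0.0679.
- Power: Φ((0.15 − 1.96 × 0.0687) / 0.0679) = Φ(0.227) = 0.59.

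**Chance of a split result when both true effects are 15 points, hospitals independent.** 2 × 0.59 × 0.41 = 0.48. Both are significant in 35% of trials and neither in 17%.

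**Sensitivity.**

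| Scenario | Power per hospital | Exactly one significant |
|---|---|---|
| N = 456, design effect 1.1 | 59% | 48% |
| Same, with continuity correction | 53% | 50% |
| N = 456, clustering ignored | 63% | 47% |
| N = 500, design effect 1.1 | 63% | 47% |
| N = 456, design effect 1.1, split 60:40 | 67% / 50% | 50% |
| N = 456, design effect 1.1, split 70:30 | 74% / 39% | 55% |

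**Independence of the hospitals.** Section 5.2 randomizes days, apparently for both hospitals together. The mixed model nests day within hospital, which supports treating them as independent. As the opposite extreme, simulated trials (60 days per arm, Poisson mean 1.9 patients per ED-day, ICC 0.1) let the two hospitals share the day effect fully. Exactly one hospital was then significant in about 43% of trials (42–45% across runs, with and without adjustment of the test for clustering).

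**What a direct comparison could show.** On the risk-difference scale, with an equal split and independent hospitals:
- SE of the between-hospital difference in effect: sqrt(2) × 0.0679 = 0.096.
- 95% CI half-width: 1.96 × 0.096 = 0.19, or 19 points.
- Difference giving 80% power: 2.8 × 0.096 = 0.27, or 27 points.
- Power for a 15-point difference: Φ(0.15 / 0.096 − 1.96) = 0.35.

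**The case against.** The plan says only that it will explore. It does not say that p-values will be compared across hospitals or that a site difference will be claimed from them. It promises odds ratios with confidence intervals, and from two such results a reader can obtain the ratio of odds ratios and an approximate standard error. All of this stands. The information is not lost; what is missing is a specified comparison.

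A reader might infer more: that site differences will be judged by significance, so that nearly half of such trials would mislead, and that the programme would then be kept at one hospital and dropped at the other. The documents do not support this. They neither state nor forbid that reading rule, so the 43–50% is conditional on it. Section 5.6 says only that sites may continue after the study, and section 11 allows closure at any site; neither ties the decision to a hospital's own result.

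It is also fair to say that an interaction test would usually miss a real difference as large as the trial's whole design effect. That limits what the change gains. It does not justify omitting the term, because its test has a nominal 5% false-positive rate and its interval shows how little two sites of this size can establish.

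**Conclusion.** The point holds as a gap in an exploratory analysis. Section 6.2 states an aim and a method that does not directly address it, and leaves the indirect comparison unspecified. The risk of a spurious split result, roughly 43–50% under identical 15-point effects, applies only if the hospital results are read by significance. It rests on an equal split, about 53–63% power per hospital, and hospitals ranging from independent to fully sharing the day effect. Departures from an equal split raise it. The pooled primary comparison and its sample size are untouched. Importance is minor to moderate.

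**What to change.** Amend section 6.2 as follows:

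- Keep the hospital-specific estimates with 95% CIs and label them descriptive.
- Add an arm-by-hospital interaction to the planned mixed model, reported with its 95% CI on that model's scale. It belongs there because section 6.2's stated primary comparison is a chi-square test, which has no place for the term. The scale must be named, since the section specifies a log link but reports odds ratios.
- If an absolute measure is wanted, add the between-hospital difference in risk differences with a cluster-adjusted CI.
- State that within-hospital p-values will not be used to claim a site difference.
- State the precision: on the risk-difference scale, a 95% CI half-width of about 19 points, 80% power only for a between-site difference of about 27 points, and about 35% power for 15 points. The 27 points is a power threshold, not the smallest difference that could reach significance, and should not be attached to the ratio-scale interaction.

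The cost is one model term with low power and a few sentences. No new data are needed.
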